40 healthy adults aged 19 to 35 years (20 men, 20 women) will participate in the study. Participants will be recruited from Western University and its surrounding community via university poster. Interested participants will be asked to come to the Exercise Nutrition Research Laboratory ([name]) for a face-to-face interview with the investigator and to complete Get Active Questionnaire (GAQ) that includes medical history for pre-screening eligibility. Inclusion criteria include healthy participants between the ages of 19 to 35 years who engage in physical activity less than three times per week. They must be able to run a mile, have an access to the gym as well as smart phones (such as Android, Cat phone, Google Nexus, Samsung Galaxy, iPhone, Microsoft Lumia, myTouch or Phablets) and can access to Apps (such as MyFitnessPal, Rise Up, Calorific, My Diet Coach, Yazio, On The Regimen, See How You Eat, Lost It, MyNetDiary or MyPlate). Exclusion criteria include diabetic, pregnant, individuals with a history of fainting, low and high blood pressure, heart disease, respiratory disease, migraines, heartburn, smokers, engage in physical activity

more than two times per week and answering YES to any questions from page 1 of GAQ. Eligible participants will be provided with the written informed consent.

Once completed, all participants will complete body composition testing via air displacement plethysmography (Bod Pod) pre and post intervention (week 0 and 6). Following Bod Pod measurements, participants will run a practice mile run for familiarity and will run again for measurement purposes before and after the exercise intervention to assess their endurance capacity. Time will be measured by a stopwatch. Participants will be match-paired based on their endurance capacity to either HIIT or MCEET group for five weeks. They will fill out two validated questionnaires, physical activity enjoyment scale (PACES) and exercise adherence rating scale (EARS) after the 6th, 9th and 15th session to assess their program adherence. They will be instructed not to engage in any either exercise program during the study period.

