All the collected data will be statistically analyzed by Sigma Plot 12.0 (Systat Software, San Jose, CA, USA) using a two-way analysis of variance (ANOVA), Tukey's post hoc test, and a paired t-test. Significance set at $p < 0.05$. Sample size estimates are generated with a two-way analysis of variance (ANOVA). The primary outcome variable is the program adherence, with a minimum important difference of 19.6 between HIIT (103.8 ± 9.4) and MCEET (84.2 ± 19.1 ; Thum, Parsons, Whittle & Astorino, 2017). Based on the data from Kadam & Bhalerao (2010), we calculate the pooled variance (19.1), effect size f (0.8), and Cohen's d (1.96) for the sample size estimation.

Using ANOVA, match-paired study design, a minimum of 15 participants is required for an alpha of 0.05 and 95% power. 34% of drop out rate (Linke, Gallo & Norman, 2011) will be included in addition to the minimal sample size resulting in 20 participants for each group.

References

- Gillen, J. B., Martin, B. J., MacInnis, M. J., Skelly, L. E., Tarnopolsky, M. A., & Gibala, M. J. (2016). Twelve weeks of sprint interval training improves indices of cardiometabolic health similar to traditional endurance training despite a five-fold lower exercise volume and time commitment. *PloS one*, *11*(4), e0154075.
- Gillen, J. B., Percival, M. E., Skelly, L. E., Martin, B. J., Tan, R. B., Tarnopolsky, M. A., & Gibala, M. J. (2014). Three minutes of all-out intermittent exercise per week increases skeletal muscle oxidative capacity and improves cardiometabolic health. *PLoS One*, *9*(11), e111489.
- Kadam, P., & Bhalerao, S. (2010). Sample size calculation. *International Journal of Ayurveda Research*, *1*(1), 55–57. <http://doi.org/10.4103/0974-7788.59946>
- Linke, S. E., Gallo, L. C., & Norman, G. J. (2011). Attrition and adherence rates of sustained vs. intermittent exercise interventions. *Annals of Behavioral Medicine*, *42*(2), 197.
- Macpherson, R. E., Hazell, T. J., Olver, T. D., Paterson, D. H., & Lemon, P. W. (2011). Run sprint interval training improves aerobic performance but not maximal cardiac output. *Medicine & Science in Sports & Exercise*, *43*(1), 115-122.
- Thum, J. S., Parsons, G., Whittle, T., & Astorino, T. A. (2017). High-Intensity Interval Training Elicits Higher Enjoyment than Moderate Intensity Continuous Exercise. *PloS one*, *12*(1), e0166299.

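### The sample size rests on matched pairs but allows for dropout person by person: at 34% dropout about 9 of 20 pairs would stay intact if the comparison is paired, and about 13 per arm if it is not, both below the required 15

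*Combined protocol and SAP*

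**What the plan says.** The allocation text in Methods states: "Participants will be match-paired based on their endurance capacity to either HIIT or MCEET group for five weeks". The exercise-programme text repeats that the matching uses the timed one-mile run.

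The statistical paragraph at the end of Methods makes programme adherence the primary outcome and takes a "minimum important difference of 19.6 between HIIT (103.8 ± 9.4) and MCEET (84.2 ± 19.1". It continues: "we calculate the pooled variance (19.1), effect size f (0.8), and Cohen's d (1.96) for the sample size estimation". The size follows: "Using ANOVA, match-paired study design, a minimum of 15 participants is required for an alpha of 0.05 and 95% power". The 34% dropout allowance "will be included in addition to the minimal sample size resulting in 20 participants for each group".

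The same paragraph lists a two-way ANOVA, Tukey's test and a paired t-test, and assigns none of them to a particular comparison. The two adherence-related questionnaires (PACES and EARS) are completed at sessions 6, 9 and 15. Nowhere does the plan say what happens to a participant whose matched partner withdraws, or whether the adherence comparison keeps the pairing.

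**The concern.** In a design powered on pairs, the unit that delivers power is the intact pair. When one member withdraws, a test that needs complete pairs also loses the partner, even one who completed everything. An allowance that counts people therefore overstates what a paired comparison retains. The plan names a matched design for its power but applies its dropout rate to individuals, so the stated 95% power may not be delivered.

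The silence on broken pairs adds a second problem. An analyst could choose between a paired and an unpaired comparison after seeing who dropped out.

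**Working it through.** **Inputs, all from Methods.** Difference 19.6; SDs 9.4 (HIIT) and 19.1 (MCEET); alpha 0.05; power 95%; minimum 15; dropout 34%, so retention 0.66; 20 per group, hence 20 pairs. The number of sides is not stated; two-sided is assumed. The 15 is read as per group, so 15 pairs, because the inflated figure is per group.

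**1. Reproducing the plan's figures.**
- Minimum size: a two-sided paired t-test with standardised paired difference 19.6/19.1 = 1.026 at 95% power needs 14.4, so 15 pairs. Power at 15 pairs is 96%. This treats 19.1 as the SD of within-pair differences. The plan does not say so; it is inferred because it returns 15.
- Dropout step: 15 x 1.34 = 20.1, hence 20 per group. This is an inflation of individuals.
- Alternatives that do not give 15: d = 1.96 gives 8 per group unpaired, or 6 pairs if used as the paired difference; f = 0.8 with two groups gives 23 in total. With the root-mean-square SD, sqrt((9.4^2 + 19.1^2)/2) = 15.05, d = 19.6/15.05 = 1.30 and f = 0.65. That d gives 17 per group by the t-test, or 16 by the normal approximation, which is close but not 15.

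**2. What 34% dropout leaves.**
- People per arm: 20 x 0.66 = 13.2.
- Intact pairs, with independent withdrawal within pairs and equal rates: 20 x 0.66^2 = 20 x 0.4356 = 8.7.
- Upper bound, partners always leave together: 20 x 0.66 = 13.2 pairs.
- Lower bound, partners never both leave: 20 x (1 - 0.34 - 0.34) = 6.4 pairs.

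Every expected value is below 15.

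**3. Power of a paired comparison at a standardised paired difference of 1.026.**

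| Intact pairs | Power |
|---|---|
| 15 | 96% |
| 13 | 92% |
| 9 | 77% |
| 6 | 53% |

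**4. If the comparison is unpaired.** About 13 per arm remain against 15. At d = 1.30 a two-sample t-test has 89% power with 13 per arm and 93% with 15.

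**5. Cost of using intact pairs only.** Per arm, 20 x 0.66 x 0.34 = 4.49 completers would be without a partner. For within-pair correlation r, the variance of the arm difference is proportional to 2(1 - r)/8.71 from pairs only, and to 2/(8.71/(1 - r) + 4.49) when single completers are kept. The standard-error ratio is sqrt(1 + (4.49/8.71)(1 - r)):
- r = 0.1: 1.21
- r = 0.3: 1.17
- r = 0.5: 1.12

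The paired-only interval is therefore about 12% to 21% wider. The correlations are assumed; the plan gives none.

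**6. Separate from the inflation formula.** Dividing by retention gives 15/0.66 = 22.7, so 23 per group. That would still leave only 23 x 0.4356 = 10.0 intact pairs under independence.

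**The case against.** The strongest reply is that the plan never commits to a paired between-arm test. The listed paired t-test has obvious within-person uses (body composition and mile time before and after the programme), and the two-way ANOVA could be group by session with independent groups. On that reading a completer whose partner withdraws stays in. This stands: the loss of partners is conditional. A reader might infer that about a third of completers (4.49/13.2) will be discarded, but the documents do not say that anyone is. The same reading does not rescue the sample size, because 13 per arm is also below 15, and the power sentence itself invokes the matched design.

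A reader might also infer bias: if MCEET loses more people, mainly HIIT completers would be unmatched. The hypothesis concerns adherence, and the plan gives no withdrawal rates by arm. Under independent withdrawal the cost is precision, not demonstrated bias.

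A third tempting figure is the 0.4% chance of keeping 15 or more of 20 pairs under independence. It is arithmetically right, but it also contains the shortfall from adding 34% where division by 0.66 was needed. It should not be charged to pairing alone.

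At the plan's stated d of 1.96, nine pairs would still give about 95% power even with no within-pair correlation. That d does not follow from 19.6 with SDs 9.4 and 19.1 (d = 1.30), and it does not yield 15.

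Finally, someone who leaves after session 6 or 9 has already given outcome data, and the 34% is not tied to a time point. This is fair, and it favours an analysis that uses partial follow-up, which the plan does not describe.

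**Conclusion.** The point holds in conditional form. The plan's 15 and its 95% power are tied to a matched design, while its dropout allowance counts individuals. At its own 34% rate, a comparison that keeps the pairing would have about 9 intact pairs, and power of about 77% against 96% at 15. An unpaired comparison would have about 13 per arm. Neither reaches the stated minimum on average.

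The figure of 9 assumes equal and independent dropout; the 6.4 to 13.2 range drops independence but keeps 34% in each arm. The 77% also rests on the inferred paired difference of 1.03. That the expected number falls below 15 does not depend on the effect size. How many completers would actually be lost cannot be settled until the plan says whether the comparison is paired.

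**What to change.** - State that a participant whose partner withdraws stays in the trial and in the analysis.
- Make the between-arm adherence comparison with a linear mixed model: arm, session and their interaction as fixed effects; matched pair and participant as random effects. It uses intact pairs, single completers and people with some of the three session measurements, and it replaces any test that needs complete pairs. Say which comparison the listed paired t-test serves.
- Restate the expected retained sample at 34% dropout, about 13 per arm and about 9 intact pairs, with the power it supports under the chosen model. Give both counts, because once single completers are kept the number of intact pairs is not by itself the effective sample size.

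The cost is analysis wording and restated figures, with no new participants or data. The drawbacks are the need for software that fits a mixed model and a less favourable stated sample and power. An unpaired analysis adjusted for mile time would also keep everyone; the mixed model is preferred because it retains the matching and handles the repeated measurements. Keeping the paired-only test and recruiting for it would be far more expensive: 15/0.66^2 = 34.4, so 35 pairs or 70 participants against 40, under the same independence assumption.

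### The 34% dropout allowance leaves about 13 per group against a minimum of 15 (read as per group), and the stated pooled variance, f and d do not follow from the quoted means and SDs

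*Combined protocol and SAP*

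**What the plan says.** All of the sizing is in the last two paragraphs of the Methods in the combined protocol and SAP.

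- **Method.** "Sample size estimates are generated with a two-way analysis of variance (ANOVA").
- **Target and source data.** The primary outcome is program adherence, with a "minimum important difference of 19.6 between HIIT (103.8 ± 9.4) and MCEET (84.2 ± 19.1"). The reference given for these figures is titled "High-Intensity Interval Training Elicits Higher Enjoyment than Moderate Intensity Continuous Exercise".
- **Derived inputs.** "we calculate the pooled variance (19.1), effect size f (0.8), and Cohen's d (1.96) for the sample size estimation".
- **Minimum.** "Using ANOVA, match-paired study design, a minimum of 15 participants is required for an alpha of 0.05 and 95% power". The text does not say whether 15 is per group, in total, or a number of pairs.
- **Dropout.** The 34% rate "will be included in addition to the minimal sample size resulting in 20 participants for each group".

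Earlier in the Methods the total is confirmed: "40 healthy adults aged 19 to 35 years (20 men, 20 women) will participate in the study". Participants are matched in pairs on endurance capacity, and they complete the "physical activity enjoyment scale (PACES) and exercise adherence rating scale (EARS) after the 6th, 9th and 15th session to assess their program adherence". The analysis sentence lists a two-way ANOVA, Tukey's test and a paired t-test, and does not say which one tests the primary outcome.

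**The concern.** Two steps can be checked from the printed figures, and neither comes out.

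First, an allowance meant to leave a required number of completers has to divide by the retained fraction. Adding 34% of the minimum to itself falls short, and the shortfall grows with the dropout rate.

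Second, the number labelled as a pooled variance is identical to one group's SD, and the two effect sizes beside it do not agree with each other or with the quoted data.

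This paragraph is the only justification for the size of the trial. If it is wrong, a reader cannot tell what power the trial has for its primary outcome, or what the 95% refers to.

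**Working it through.** **Inputs, all from the sample size paragraph:** difference 103.8 - 84.2 = 19.6; SDs 9.4 (HIIT) and 19.1 (MCEET); stated pooled variance 19.1, f = 0.8, d = 1.96; alpha 0.05; power 95%; minimum 15; dropout 34%; 20 enrolled per group. Sidedness is not stated and two-sided is assumed. Power figures use the noncentral t distribution.

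**1. Reproducing the 20.** 15 x (1 + 0.34) = 20.1, which matches the stated 20 per group. This is also the evidence that 15 means per group: a total of 15 does not lead to 20 in each group.

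**2. What 20 delivers.**
- Completers per group: 20 x (1 - 0.34) = 13.2, below 15.
- Enrolment needed to keep 15: 15/0.66 = 22.7, so 23.
- Largest loss at which 20 still leaves 15: 1 - 15/20 = 25%.

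**3. Effect size from the quoted data, as two equal independent groups.**
- Pooled variance: (9.4² + 19.1²)/2 = 226.6, so the pooled SD is 15.05.
- d = 19.6/15.05 = 1.30. For two groups f = d/2 = 0.65.
- The stated pair conflicts: f = 0.8 means d = 1.6, and d = 1.96 means f = 0.98.
- Other SDs do not rescue it: 9.4 gives d = 2.09, 19.1 gives 1.03, and the mean SD of 14.25 gives 1.38.

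**4. Does 15 follow?** Smallest n per group for 95% power, two-sided two-sample t-test:

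| Input | n per group | Power at that n | Power at n - 1 |
|---|---|---|---|
| Stated f = 0.8 (d = 1.6) | 12 | 96.3% | 94.6% |
| Stated d = 1.96 | 8 | 95.4% | 91.9% |
| Recomputed d = 1.30 | 17 | 95.7% | 94.5% |

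None gives 15. A two-sided paired t-test with SD of differences 19.1 does give 15 pairs (95.8%, against 94.3% at 14), but the plan states no such route.

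**5. Power after 34% loss.**

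| Analysis | Number remaining | Power |
|---|---|---|
| Two-sample, d = 1.30 | 13 per group | 89% |
| Two-sample, 19.1 as common SD (d = 1.03) | 13 per group | 71% |
| Paired, SD of differences 19.1 | 13 pairs | 92% |
| Paired, SD of differences 19.1 | 9 pairs | 77% |
| Paired, quoted SDs, within-pair correlation 0 to 0.5 | 9 pairs | 68% to 87% |
| Two-sample, stated f = 0.8 | 13 per group | 97% |
| Two-sample, stated d = 1.96 | 13 per group | over 99% |

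Thirteen completers per group form 13 intact pairs only if the losses fall in the same pairs. If dropout is independent between pair members (an assumption), the expected number is 20 x 0.66² = 8.7, about 9 pairs. In the row with a correlation range, the SD of differences is √(9.4² + 19.1² - 2 x r x 9.4 x 19.1), which is 21.29 at r = 0 and 16.54 at r = 0.5.

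**6. Using all three assessments.** If d = 1.30 holds at each of sessions 6, 9 and 15 and their mean is compared, the effective d is 1.302/√((1 + 2ρ)/3). Power at 13 per group is then 97% at ρ = 0.5 and 93% at ρ = 0.8. The plan states no within-person correlation.

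**The case against.** The strongest defence is that the dropout step by itself costs nothing on the plan's own inputs: at the stated f or d, 13 per group still exceeds 95% in a two-sample test. That stands. The loss appears only when the inputs are recomputed or a paired analysis is used.

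A second defence is that leavers are not necessarily missing. Adherence is the outcome, and questionnaires are taken at sessions 6 and 9 as well as 15, so someone who leaves late may contribute data. Averaging the assessments would also help. This stands too, and softens the loss, but the plan does not say which assessment is primary.

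A third is that the recomputed d treats the quoted SDs as those of two independent groups and assumes that they apply to the adherence measure. The design of the cited study is not visible in the documents, and its title concerns enjoyment. This makes every power figure conditional. It does not rescue a pooled variance equal to one group's SD, or a two-group f and d that contradict each other.

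Two stronger readings are tempting. A reader might infer that the minimum of 15 is simply wrong. The documents do not show that, because a paired calculation reaches 15; what they show is that 15 does not follow from the stated f or d in a two-group comparison. A reader might also infer that the trial must enrol 23 per group. That figure holds only if 15 survives re-derivation. With a two-sample test at d = 1.30 the minimum is 17, and 17/0.66 = 25.8 gives 26.

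**Conclusion.** The point holds. Reading 15 as per group, the dropout allowance misses the plan's own minimum by about two completers per group, and 20 enrolled tolerates 25% loss, not 34%. The stated pooled variance, f and d do not follow from the quoted means and SDs, and the basis of 15 is not given.

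The size of the consequence cannot be fixed at one number, because the plan names neither the primary test nor the handling of incomplete pairs. With the inputs recomputed and 34% loss, power is 89% for a two-sided two-sample comparison at d = 1.30. For complete pairs at SD of differences 19.1 it lies between 77% (about 9 pairs) and 92% (13 pairs). It would be 71% if 19.1 were the common SD in a two-sample test.

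It would go too far to call the trial invalid or clearly underpowered, since some defensible analyses keep power at 93% to 97%. It would equally go too far to call the loss modest throughout, since that assumes intact pairs or an unpaired test. All the power figures assume that the 19.6 difference and the quoted SDs apply to the primary measure.

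**What to change.** Rewrite the sample size paragraph, without adding participants.

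1. **Inputs.** Confirm that the cited means and SDs apply to the adherence measure used as primary. If they do, replace the inputs with pooled SD 15.05 (variance 226.6), d = 1.30 and two-group f = 0.65. If they do not, justify inputs for that measure first.
2. **Test.** Name the primary test, consistently with the matched design. Give its sidedness, the assessment used (session 6, 9, 15 or their mean), any assumed within-pair or within-person correlation, and how incomplete pairs are handled. Re-derive the minimum for that test and say whether it is per group or a number of pairs.
3. **Dropout and power.** Inflate by n/(1 - 0.34). This gives 23 per group only if the minimum stays 15, and 26 if it becomes 17. Keep 20 per group, and replace the 95% claim with the power of the named test at the expected number of completers (about 13 per group) or of intact pairs (about 9 to 13).

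The cost is one rewritten paragraph and a commitment to the primary test in advance. The downside is a less favourable stated power.

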The first week of the exercise intervention will consist of one-on-one supervised treadmill training, three times per week in the lab. From week two to five, participants will follow the same exercise program on their own at their preferred gym three times per week in order to examine free-living individuals adhere to two exercise programs. Each participant will be matched to either HIIT or MCEET group based on their timed one-mile run. The HIIT group will perform six, 20-second bouts of high intensity interval exercise separated by 2 minutes of active recovery (walking) while the MCEET group will perform 14 minutes of continuous endurance exercise at 70% Maximum Heart Rate (MHR). Both exercise protocols will include 3 minutes of warm up and cool down at a 30% MHR, for a total of 20 minutes for each treatment.

Ratings of perceived exertion (RPE; Borg CR-10 scale) will be recorded at the end of each interval for HIIT group and at 10 and 20 minutes of exercise for MCEET group on the 6th, 9th and 15th session. All participants will log their heart rate before, during, and immediately after each training session using Fitbit or a free heart rate monitor mobile App (e.g. Argos) to ensure safety and achievement of their targeted heart rate. Participants will also complete physical activity enjoyment scale (PACES) and exercise adherence rating scale (EARS) on the 6th, 9th and 15th session to assess their program adherence. To accommodate progression, training intensity will be adjusted to maintain the desired relative exercise intensity based on above measurements. Finally, no attempt will be made to modify the participants daily diet, but a 3-day food log will be collected via free mobile app (e.g. MyFitnessPal) to assess food intake for any change. Completed questionnaires and the recorded heart rate data saved on Fitbit or a mobile app will be used to confirm program adherence.

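### Program adherence is the primary outcome, but nothing in the plan brings stopping the programme into the primary comparison, so unequal dropout could hide or reverse the arm difference

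*Combined protocol and SAP*

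**What the plan says.** The statistical paragraphs at the end of Methods state: "The primary outcome variable is the program adherence". The description of the intervention says that weeks two to five are left unsupervised, at the participant's own gym, "in order to examine free-living individuals adhere to two exercise programs". Whether people keep going is therefore what the trial sets out to learn.

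Adherence is assessed with two questionnaires, PACES and EARS, completed after the 6th, 9th and 15th sessions. Heart rate is logged at every session. Those logs and the questionnaires are to be used to confirm adherence, but no scoring rule is given for the logs.

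Dropout appears once, in the sample size. The basis is: "Using ANOVA, match-paired study design, a minimum of 15 participants is required for an alpha of 0.05 and 95% power". A 34% dropout allowance "will be included in addition to the minimal sample size resulting in 20 participants for each group".

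The analysis text says that everything collected will be analysed by two-way ANOVA, Tukey's test and a paired t-test. It names no analysis population, gives no rule for missing questionnaires, and does not say whether a person who stops counts as non-adherent.

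**The concern.** In most trials a dropout is a missing outcome. Here, stopping the programme is itself information on the primary outcome, and usually evidence of poor adherence. Adding people to replace those expected to leave restores numbers but does not record that they left.

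The measurement schedule works the same way. A questionnaire tied to reaching a given session cannot be completed by someone who never reaches it. A score from session 6 or 9 describes the person before they stopped.

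The hypothesis is that HIIT is adhered to better than MCEET, so unequal dropout is a result the trial itself expects. If it occurs, the group with more stoppers is represented at session 15 by its more persistent members. The difference in adherence can then shrink, vanish or change sign. If the rule stays open, it will be chosen after dropout by arm is known.

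**Working it through.** **Inputs from Methods.** Minimum 15; dropout 34%; 20 per group, 40 in total; three sessions a week for five weeks, so 3 × 5 = 15 sessions; scores "between HIIT (103.8 ± 9.4) and MCEET (84.2 ± 19.1"; difference 19.6.

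**1. The plan's own figure.** 15 × (1 + 0.34) = 20.1, which gives the stated 20 per group. The minimum of 15 matches a two-sided paired t-test with 19.1 as the SD of the differences: 19.6 / 19.1 = 1.026, for which 15 pairs give 95.8% power. So 15 is a count of people or pairs with scores, and the extra five per group replace people expected not to count.

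**2. How many are affected.** 40 × 0.34 = 13.6 people leave (6.8 per group), and 20 × 0.66 = 13.2 per group remain. That 13.2 is below 15 is a separate point about how the allowance was applied.

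**3. What each person contributes under the plan.**

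| Last session done | Questionnaire scores | Is stopping recorded in the score? |
|---|---|---|
| Before 6 | none | no |
| 6 to 8 | session 6 | no |
| 9 to 14 | sessions 6 and 9 | no |
| 15 | all three | did not stop |

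**4. Direction of the bias.** Illustrative assumptions, not from the documents: in the first case those who finish do 13 of 15 sessions in both arms; those who stop do 5.

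- *Hidden difference.* Dropout 24% HIIT, 44% MCEET. HIIT: 0.76 × 13 + 0.24 × 5 = 11.08. MCEET: 0.56 × 13 + 0.44 × 5 = 9.48. The true difference is 1.6 sessions; among finishers it is 0.
- *Reversed difference.* Finishers do 13.5 (HIIT) and 12 (MCEET); dropout 44% and 24%. HIIT: 0.56 × 13.5 + 0.44 × 5 = 9.76. MCEET: 0.76 × 12 + 0.24 × 5 = 10.32. The true difference is −0.56; among finishers it is +1.5.

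**5. Power, by simulation.** Pooled SD = √((9.4² + 19.1²) / 2) = 15.05; d = 19.6 / 15.05 = 1.30. Scores are normal with that separation and equal SDs, 20 per arm. A person drops out when score plus random noise falls below the cut-off that gives 34% dropout overall. More noise means a weaker link between dropout and adherence. The worst-rank test keeps all 40 and ranks stoppers lowest. With all 40 scores known, power is about 98%.

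| Link between dropout and score | Completers' t-test | Worst-rank test, all 40 |
|---|---|---|
| Strong (noise 0.5-1.0 SD) | about 60-73% | about 90-95% |
| Noise 2 SD | about 83% | about 78% |
| Noise 3 SD | about 85% | about 67% |
| None | about 88% | about 36% |

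Under the strong link, dropout is about 14-18% in HIIT and 50-54% in MCEET, and the completers' difference falls from 1.30 to about 0.77-0.96 SD. The simulation ignores scores left at sessions 6 and 9, so it describes a comparison of those who stay to the end.

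**The case against.** A reader might infer that the primary comparison is made only among people who adhered. The documents do not support that. No completers-only set is written, and the analysis text covers everything collected. An allowance in the sample size is not an exclusion rule, and the same participants also supply week-6 body composition and mile-run data, where a dropout really is lost data. People who stop after session 6 or 9 leave scores, heart-rate logs cover the sessions they did, and people who stay can still score low on EARS.

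Nor can it be said that stopping is already known for all 40. Weeks two to five are unsupervised and self-logged. The plan has no record of a stop date and does not separate stopping exercise from stopping logging or leaving the study. Some people will leave for reasons unrelated to adherence.

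The size is also uncertain. The standardised difference comes from a cited study whose title concerns enjoyment, and the link between dropout and adherence is assumed. Under a weak link the worst-rank test loses power against the completers' test, so it cannot be presented as a free improvement.

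All of this stands, and it limits the point. It does not remove it: earlier scores record adherence before stopping, the logs have no scoring rule, and no sentence brings stopping into the primary result.

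**Conclusion.** The point holds in limited form. The plan does not say how people who stop enter the primary adherence outcome and, as budgeted and measured, the stopping itself does not enter it. This concerns about a third of the sample by the plan's own figure.

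The possible bias runs both ways: a real difference can be hidden, or its sign reversed, when dropout differs between arms. If dropout is equal and unrelated to adherence, the cost is mainly lost precision. The session counts and power figures are illustrations that rest on assumed dropout by arm, assumed sessions among stoppers and an assumed link between dropout and score. They are not predictions for this trial. The conclusion that a rule is needed rests only on the outcome, the questionnaire schedule and the dropout allowance.

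**What to change.** In the statistical paragraphs of Methods:

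1. Analyse all 40 participants as allocated, on an adherence measure defined for everyone. One suitable choice is sessions completed out of 15, taken from the supervised week-1 sessions and the heart-rate logs already collected. People who stop are credited only with the sessions they did.
2. Report the number who stopped in each arm, with a confidence interval for the difference, as part of the primary adherence result.
3. Keep the questionnaire-score comparison as a supporting analysis, and say which of the three time points it uses.
4. Treat a worst-rank analysis as an optional sensitivity analysis, given its power loss when dropout is only weakly related to adherence.

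Cost: plan wording and one further analysis, with no extra participants or visits. The date of the last logged session must be extracted from the logs. People who stop logging, or who leave for unrelated reasons, may count as non-adherent, so recorded reasons would help interpretation. The 19.6-point difference is on a questionnaire scale and exceeds the 15-session maximum, so it cannot describe the new measure. A new planning difference is needed, and the documents give no figure from which to recompute the sample size.
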